Since this study is dealing with unknown clinical endpoints, determination of a disease state by statistical methodology is a prime thrust of the investigation. Inferences about a disease state will be developed by identifying symptom complexes or physical findings which in themselves may represent disease. By comparison of symptoms, signs and laboratory tests within and between groups, a logical decision-making scheme can be utilized to calculate relative risks from baseline data. If appropriate, these results will be used to sharpen adaptive approaches in the follow-up study. By the use of combinational and correlational analysis, statements about the probability of a disease state, a subclinical state, and/or over-reporting bias will be attempted. In addition, the application of regression techniques to a normalized exposure index among exposed individuals exhibiting symptoms and/or signs will also assist in the determination of a disease state. Beyond these pair-wise and group comparisons, newer techniques of pattern recognition, such as Factor Analysis and Cluster Theory, are being considered in order to achieve a more automatic and objective analysis. Mortality data will be analyzed using several different approaches, including age and age-disease specific rates, standardized mortality rates and modified life table approaches, as well as more sophisticated logistic and multiplicative models (survival analysis). Analysis of questionnaire and physical examination data will utilize log-linear models to verify the appropriateness of the standard statistical methodologies (e.g., McNemar's test for dichotomous rates). Polytomous or categorical findings will be analyzed by the use of log-linear models. Continuous variables will undergo covariance analysis to remove non-controlled effects, followed by the use of a paired difference statistic. Some data will naturally fall into groups (e.g., fertility/reproduction, liver function tests) in which case, multiway contingency table analysis or extensions of the generalized linear model analyses will be used.

PROJECT RANCH HAND II

EPIDEMIOLOGIC INVESTIGATION OF HEALTH EFFECTS
IN AIR FORCE PERSONNEL FOLLOWING EXPOSURE TO HERBICIDE ORANGE

MATCHED COHORT DESIGN

I. Purpose of the Investigation

The purpose of this investigation is to determine whether long-term health effects exist and can be attributed to occupational exposure to Herbicide Orange through the use of epidemiologic techniques.

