²individual not assigned specifically to RH, although may have serviced the aircraft; denominator not ascertainable

³"Morning Reports" may permit ascertainment of this group.

Because of the significant combat hazard associated with low, slow flying missions, all early RANCH HAND crewmembers were elite volunteers (see Risk-Taking Bias, Section VIII). In fact, RANCH HAND crewmembers comprised one of the most highly decorated units during the RVN Conflict. Anecdotal stories reveal that most crew members were, on occasion, heavily exposed to Herbicide Orange due to normal or combat induced equipment malfunctions within the aircraft. Many former RANCH HAND personnel are expected to be currently employed in the aerospace industry as commercial airline pilots, airline managers, and flight mechanics. RANCH HAND personnel still on active duty are expected to be found in senior management positions.

(2) Ancillary Study Groups (Non-RANCH HAND personnel)

Air Force handlers of herbicide drums in RVN were exposed to herbicides because of drum leakage. Advertisements

similar to those proposed for the RANCH HAND personnel may be issued in attempts to define this population. As the drum handlers were ad lib participants, no personnel designator was assigned to these individuals, thus prohibiting computer tracking and identification. The population is unknown, but expected to be small (less than 200) as the majority of drum handlers were known to be Vietnamese. Additional groups such as US Army personnel (officer and enlisted) who flew as observers, US Army helicopter crews, as well as experimental fighter-bomber spray personnel, may be included in the study. Specific epidemiologic/clinical studies for these groups must be planned by a separate protocol following their ascertainment since control group selection will be difficult or moot. It is intended that all data derived from the ancillary study groups will be subsetted for separate analysis and these data will be treated as anecdotal to the primary study.

The members of these groups are expected to be males, ranging in age from 28-68 years. The officer/enlisted ratio is estimated at 1:10. Approximately 10-18% of these populations are expected to be Black. Low numbers of respondents are expected and population at risk ascertainment will not be possible.

(3) Control Group (Not exposed to Herbicide Orange)

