| (2) Crew Chiefs, Aircraft Mechanic, and other Support Personnel: | moderate potential |
| (3) Console Operators and Flight Engineers: | high potential |

The "pilot" group probably received most of their exposure during pre-flight checks as well as during the actual dissemination missions. The crew chief group experienced contact with herbicides during dedrumming and aircraft loading operations as well as during on-site repair of the aircraft and spray equipment. The console operator group was exposed while supervising the loading of the aircraft, during ground testing the equipment, and by tank leakage during dissemination missions.

The available historical records on Operation RANCH HAND indicate that personnel assigned to the project seldom had a "routine" work schedule or environment, thus complicating estimates of the level of herbicide and dioxin exposure. Since actual exposure data (e.g., mg of herbicide/kg body wt) are not available, the establishment of an exposure index will be attempted. The exposure index will be calculated for each RANCH HAND individual to obtain a standardized frequency distribution. The exposure index will be calculated by evaluating the known factors that would have influenced exposure. For aircrew members, these will include such factors as:

- (1) Date of tour with RANCH HAND in Vietnam.
- (2) Number and lengths of tours in Vietnam with RANCH HAND.
- (3) Number of herbicide dissemination missions (as reflected by flying hours and air medals).
- (4) Herbicides employed (yearly records are available that reflect the amount of each herbicide sprayed).
- (5) Crew position.
- (6) Routes of exposure (the major route of exposure for most RANCH HAND personnel was probably percutaneous, although for the console operator, exposure through inhalation may have also been significant).

An exposure index may be derived from consideration of the above factors, i.e., it is a function of those factors:

$$E_I = f(D, T, P, C, R, H),$$

where E_I = Exposure Index

D = Dioxin Concentration Estimate During RANCH HAND Tour

The date of tour with RANCH HAND is important since mean dioxin concentrations in the herbicides changed by a factor of 16 between pre-1965 and post-1965. In 1965, both high and low dioxin formulations were available. Thus, a scale of values for TCDD are:

Pre-196532
196516
Post-19652

T = Duration of Exposure/Number of Missions Flown

P = Proportion of 2,4,5-T Herbicides Used

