The ratio value of the amount of 2,4,5-T containing Herbicide applied for any given year against total amount of the herbicide applied during the same year. Data on herbicide expenditures by year are available. For example in 1962, Purple comprised 88 percent of all herbicides used that year, while in 1966, Herbicide Orange accounted for 66 percent of the total amount of herbicide applied.

C = Crew Position/AFSC

Relative exposure values for this factor will be determined by separate studies.

R = Route of Exposure

Relative values for exposures via ingestion, inhalation or percutaneous absorption will need to be evaluated from literature, computer modeling, and inflight determinations using a Herbicide Orange simulant.

H = Exposure History

A relative value based upon the subject's preception as to the magnitude of his own exposure. This will be obtained from the questionnaire and may reflect no exposure, a light exposure, a moderate exposure or a heavy exposure. A weighted value will be assigned to each exposure estimate, if possible.

(2) Proposed Studies

Within the exposure index equation, relative exposure values for two factors are lacking; crew position within the C-123 aircraft and the route of exposure. Approaches which will be used in obtaining estimates for these two factors include (1) use of a diffusion model which would consider the internal aircraft volume and configuration in computing specified source strengths and concentration levels; (2) use of quantitative data obtained at specified points within the aircraft following actual C-123A/A 45Y-1 dissemination missions using a Herbicide Orange Simulant; and (3) use of a combination of the above two methods. Discussion with personnel of the U.S. Army Environmental Hygiene Agency and the Chemical Systems Laboratory, Edgewood Area, Aberdeen Proving Grounds, Maryland, suggest that the dispersion of herbicide vapors and particles within the C-123 aircraft could be modeled provided data could be obtained for selected parameters. These parameters include:

- (1) Air flow measurements within the aircraft under flying conditions simulating those encountered during actual RANCH HAND missions.
- (2) Physical properties of Herbicide Orange components.
- (3) Internal volume of aircraft and individual compartments.
- (4) Temperatures of internal surfaces.
- (5) Estimate of surface area on the floor of the aircraft.

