Exposure estimates will be used to sharpen the statistical analysis and can be helpful in summarizing responses. In this discussion, two estimates will be considered: one related to Vietnam herbicide exposure, and another related to domestic (US) herbicide exposure independent of Vietnam experience.

Vietnam herbicide exposure. In the above discussion of statistical methodologies, exposure variables appeared. In the logistic formula on page VI-8, the variable E was shown which could

be either dichotomous, polytomous, or continuous. In the use of logistic functions to discuss study power, the exposure variable was taken as dichotomous. When a polytomous or continuous exposure variable E is constructed, significant sharpening of the study analysis will be accomplished. For example, biases in this study could lead one to suspect that differences between RANCH HAND personnel and controls were in fact due to factors other than a herbicide effect. If however, in addition to differences between RANCH HAND personnel and controls, one was able to show a regression of mortality and/or morbidity on an exposure index E , the case for a bonafide herbicide effect would be firmer. The reconstruction of exposures is discussed in Section V, G.

Domestic herbicide exposure. Individuals in both the RANCH HAND and control groups will have had varying exposure to herbicide in the United States. Particularly, individuals from specific farming and/or foresting areas, may have had and continue to have a significant background exposure. Data on place of residence and information concerning home practices (gardening etc.) could be used to build a background exposure index E_b . In lieu of constructing this index, stratification techniques will be used in the analytic phases of the study.

I. The Replacement Concept

In the mortality analysis, a randomly selected group of control individuals will be compared to the RANCH HAND group, and the data gathered will be analyzed for evidence of herbicide effect. In the questionnaire and physical examination phases of this study, one of the mortality controls will be randomly selected for each RANCH HAND individual. During the physical examination phase, we must anticipate a significant degree of unwillingness to participate, particularly on the part of control personnel. This loss to study can result in significant bias and loss in statistical power; thus the replacement concept has been developed to mitigate these consequences.

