False positive response is anticipated as the primary bias operating in this study. Compensation issues arising from individual claims to the VA or from class action suits, heightened health concern generated by extensive publicity, disenchantment with military service, and the simple desire to please the interviewer may introduce positive responses that exceed the study's ability to correct or adjust. False negative response will also operate, and such bias is even more difficult to assess than the spurious response in a positive direction. Significant factors in this direction include: issues of patriotism and loyalty, personal conviction as to the propriety of the defoliation program and their participation in it, the strong virility orientation of the pilot/aircrew population (particularly with reference to questions of libido and fertility), personal inconvenience caused by study participation, errors of memory, and fear of the adverse effects on career goals that abnormal physical examination results could produce (a significant problem for active civilian and military pilots).

(2) Pending Retirement Bias

The military retirement system also creates a potential source of bias. A "pending-retirement phenomenon" occurs when personnel who are approaching the end of their careers exaggerate their symptoms so that they may become eligible for disability benefits.

(3) Corrective Measures

The primary correction technique for questionnaire response bias will be a carefully constructed and standardized physical examination. Multiple verification and bias indicator questions will be designed and included in the initial questionnaire. Memory verification will be conducted by cross-referencing responses

to medical and personnel records. Detailed statistical correlations between the questionnaire responses and the physical examination results will be conducted. All telephone interviews and physical examinations will be conducted on a "blind" basis to the maximum extent possible. Self-administered and group-administered questionnaires, which would allow for uncontrolled response changes, will not be conducted. Models of anticipated biases and their estimated impact on the study will be attempted prior to the final analysis of any phase in order to justify the analytic methods used. Conclusions drawn from this study will be predicated and coupled to a bias estimate.

E. Interview Bias

(1) Problem

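### The exposure index includes each man's own estimate of his exposure, so a dose-response on self-reported symptoms cannot serve as independent evidence against over-reporting

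*Protocol*

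**What the plan says.** Section V.G(1) introduces the index as built from objective circumstances: "The exposure index will be calculated by evaluating the known factors that would have influenced exposure". It lists six for aircrew: tour dates, number and length of tours, missions, herbicides used, crew position and route of exposure. The formula that follows, E_I = f(D, T, P, C, R, H), adds a term that is not on that list. H scores the subject's "preception as to the magnitude of his own exposure. This will be obtained from the questionnaire". Its source and grades are given in full: "This will be obtained from the questionnaire and may reflect no exposure, a light exposure, a moderate exposure or a heavy exposure". A weight is to be attached if possible. The function f and all weights are left open.

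Section VI.A takes the symptom data from the questionnaire as well. The index then has two evidential uses:

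- Section V.F(2) names a positive exposure index, together with positive verifiers and negative bias indicators, as something that substantially lowers the probability of over-reporting.
- Section VI.H considers the suspicion that group differences come from bias. It says that if mortality or morbidity also regresses on E, "the case for a bonafide herbicide effect would be firmer".

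Section VIII.D(1) states: "False positive response is anticipated as the primary bias operating in this study". Section V.G(2) describes a cruder index without H, based on duration of duty and TCDD concentration, but only in case the fuller index proves infeasible.

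**The concern.** An internal dose-response helps against reporting bias only if the exposure score is free of that bias. H is not. Compensation, publicity and health worry, which section VIII.D(1) gives as reasons for false positive symptoms, are equally reasons to rate one's exposure as heavy. Both answers come from the same man in the same questionnaire. A gradient of reported symptoms on E_I could then arise with no herbicide effect and be read as support for one.

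There is also a problem of fit. Section VI.H wants mortality regressed on E, but men already dead cannot state their perceived exposure, nor can those who do not answer the questionnaire.

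**Working it through.** The protocol states no sample size, power or alpha for the exposure-index regression, so there is no planned figure to reproduce. The check is a reading of the text plus two illustrations under no herbicide effect.

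**Inputs from the protocol**
- Exposed population about 1200 (V.B(1)); 65% questionnaire response and 40% examined (VIII.G(1)).
- n = 0.65 × 1200 = 780 for questionnaire outcomes; 0.40 × 1200 = 480 for examination outcomes. Expected non-response to the questionnaire: 100% − 65% = 35%.

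**Assumptions (not in the protocol)**
- Two-sided alpha of 0.05, as in the power tables.
- A latent reporting tendency with correlation r to the symptom score and the same r to H.
- H supplies a share s of the variance of the index; the rest of the index is unrelated to reporting.

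**Illustration 1, analytic**

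Correlation of symptom score with H: r × r = r². Correlation of symptom score with index: c = r²√s. Fisher z shift: d = atanh(c) × √(n − 3). False-positive rate = P(Z > 1.96 − d) + P(Z < −1.96 − d).

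Worked case, r = .3, s = .25, n = 780: c = .09 × .5 = .045; d = .04503 × √777 = .04503 × 27.87 = 1.255; rate = P(Z > .705) + P(Z < −3.215) = .2404 + .0007 = 24%.

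| r | s = 10% | s = 25% | s = 50% |
|---|---|---|---|
| .1 | 5.1% | 5.2% | 5.4% |
| .2 | 6% | 9% | 12% |
| .3 | 12.5% | 24% | 43% |
| .4 | 29% | 61% | 89% |

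(n = 780.) At n = 480 and r = .3 the rates are 10%, 17% and 29%. Section VI.B(1) puts the cohort nearer 1000, which would give 650 respondents and rates between those for 480 and 780.

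**Illustration 2, simulation**

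This used 2,000 runs per setting, with a four-grade H and an index formed as an equal-weight sum or a log product of six components. It counted only positive gradients with z > 1.96, so the nominal rate is 0.025. Here rho is the weight of the reporting tendency in perceived exposure, and b its log odds ratio per SD on symptom reporting.

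| Setting | n = 450 | n = 780 |
|---|---|---|
| rho .2, b 0.4 | 0.037–0.046 | 0.052–0.059 |
| rho .3, b 0.7 | 0.086–0.116 | 0.118–0.160 |
| rho .5, b 0.7 | 0.158–0.226 | 0.229–0.360 |
| rho .5, b 1.0 | 0.252–0.383 | 0.400–0.606 |

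(Self-reported symptom, H in the index; ranges run across the two index forms.)

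- H removed: 0.018–0.033 in every setting, that is, nominal within simulation error.
- Objective sign unrelated to reporting tendency, H in the index: 0.016–0.033, so no inflation.
- Objective sign, but men who have it overstate exposure (assumed weight 0.1 to 0.3, n = 450): 0.108–0.581 for the sum and 0.156–0.745 for the product.

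**The case against.** The strongest reply is that the index does not carry the burden alone. Section VIII.D(3) names the standardized physical examination as the primary correction for response bias and adds verification questions, bias indicators and record checks. Section V.F(2) uses the index only alongside such items, and section VI.H claims only a firmer case, in addition to a group difference. All of this stands. A reader might infer that the dose-response is the plan's main safeguard, or that it is meant to rule bias out; the text supports neither.

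A reader might also infer that bias sits on both sides of every dose-response regression. It does so only for self-reported outcomes. Section V.F(2) frames the dose-response on physical signs and/or verifiable symptoms, and section V.D(4) blinds examiners to group. These protections act on the outcome, however. None acts on H, so differential recall by ill men remains possible.

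Two further readings go too far:

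- The Executive Summary speaks of "regression techniques to a normalized exposure index among exposed individuals exhibiting symptoms and/or signs", which sounds like selection on the outcome. Section V.G(1) computes the index for every RANCH HAND man, and section V.F(2) correlates it with the presence of signs, which needs men without signs too. This is a wording mismatch.
- Crew position follows rank, and the dioxin term follows an era in which "all early RANCH HAND crewmembers were elite volunteers". The regression is nevertheless not left unadjusted: V.G(2) offers stratification by AFSC, and VI.C and VI.E provide for risk-taking and AFSC adjustment.

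Finally, the index and the weight for H are tentative in the text, and inflation is slight at correlations of .2 or below unless H dominates the index. That limits what can be said about size, but it does not justify including H.

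**Conclusion.** The point holds in a limited form. As written, H belongs to the index, comes from the same instrument as the symptoms, and is nowhere separated out; the version without H is kept only for infeasibility. For self-reported outcomes, a gradient on this index is not independent evidence against over-reporting. For blinded signs and laboratory values the risk is conditional on ill men recalling heavier exposure. For mortality, an index needing H cannot be computed for men already dead.

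The size is not known. Over the assumed range, a nominal 5% error runs from essentially 5% (r = .1) to 89% (r = .4, H half of index variance). The correlations, the share of H and the alpha are all assumptions. The direction of the bias, and its disappearance when H is removed, do not depend on the exact values chosen, provided the other terms are unrelated to individual reporting tendency.

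**What to change.** Define the main exposure variable as the index from D, T, P, C and R, without individual self-perception, and use it in all dose-response analyses, mortality included. Still collect H. Compare it with the main index as a bias indicator, and let it enter an index only in a labelled sensitivity analysis.

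State that the regression covers all RANCH HAND men, as sections V.F(2) and V.G(1) imply, and align the Executive Summary wording. Adjust for or stratify by AFSC and tour era with the methods already planned in V.G(2) and VI.E.

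No new data are needed. The cost is that a man's own recall of his exposure no longer sharpens the main index. The remaining index is not wholly free of recall either: section V.G(2) takes spill frequency and size from RANCH HAND recollection, so C and R still rest partly on memory, though as group-level values rather than each man's rating of himself.
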